Title: Mechanisms of Fall Resistance to Diverse Slipping Conditions

NCT03758040

11 Mar 2021

Study Protocol

For all gait collections, participants will arrive at the Biomechanics Research Building on the University of Nebraska at Omaha campus. All participants will be consented and screened prior to gait testing. During the consent process, participants will be asked if they can be contacted again for future research studies. During the screening, participants will undergo a short medical history.

Participants will be asked to put on a form fitting suit for data collection. Body weight, height and extremity anthropometry will be collected (length of arm and leg segments). Retroreflective markers will be placed on the legs, arms, torso and head to obtain whole-body kinematic data. A ceiling-mounted safety harness will also be fitted to each participant. Prior to performing any walking trials, the participants will be allowed to "sit" in the harness to experience how it feels when it catches them.

Aim 1 Specific Methods

Young healthy participants will undergo overground gait and stabilization movement analysis sessions that will last approximately 210 minutes. All participants will be fitted with a form-fitting singlet, ceiling mounted safety harness, lab-provided shoes, and a full-body retroreflective marker set. A load cell placed in line with the safety harness will allow for the quantification of forces exerted on the harness at 80 Hz. A 17 camera 3D motion capture system will be used to collect kinematic data at 120 Hz throughout each trial. Data will be collected at a comfortable walking speed of 1.3 m/s. Walking speed will be monitored using timing gait plates placed along the path. Participants will be coached to maintain prescribed walking speed. A repeated measures design will have participants slip both feet at 3 different times in the gait cycle for each of 3 path curvatures for a total of 18 slip episodes. Slips will be delivered while walking along a straight path (infinite radius), or curved paths with radii of 2 or 1 meters. A path consisting of multiple turns will be marked on the floor of the lab, including turning radii of 2 and 1 meters.

Only right turns will be examined, as previous research has found no difference between the kinematics of left and right turns. Participants will follow the path for a randomly selected amount of time between 1 and 3 minutes. After this time has elapsed, the investigator will initiate a slip during a randomized turn on the path in early, middle, or late stance. Participants will be given a seated rest period of 5 minutes between each trial.

Aim 2 Specific Methods

Young healthy participants will undergo treadmill gait and stabilization movement analysis sessions that will last approximately 270 minutes. All participants will be fitted with a form-fitting singlet, a safety harness mounted to the rigging of the CAREN system, lab-provided shoes, and a full- body retroreflective marker set. A load cell placed in line with the safety harness will allow for the quantification of forces exerted on the harness at 80 Hz. Data will be collected with the treadmill set at a comfortable walking speed of 1.3 m/s. A repeated measures design will have participants slip at 3 different times in the gait cycle for each of 5 different uphill/downhill slopes and at 3 times to both feet for 2 cross-slopes for a total of 27 slip episodes (3 phases x 5 slopes that foot doesn't matter + 3 phases x 2 feet x 2 slopes that foot matters).

Specifically, slips will be delivered over sloped ground surface of no slope, ± 5.0 and ± 10.0 degrees slopes in the direction of walking, and 5.0 and 10.0 degrees perpendicular to the direction of walking.

Sloped surfaces will be generated with the CAREN system treadmill, which is capable of pitch and roll ± 16 degrees.⁵⁵ Slip onset will be triggered by the experimenter in a randomized order at early, mid, or late stance. Participants will walk on the prescribed slope and a slip will be triggered on after a randomly predetermined amount of time between 1 and 3 minutes at either early, middle, or late stance.

Participants will be given a seated rest period of 5 minutes between each trial. To quantify the effects of the slip perturbation, whole body angular momentum, COM characteristics, arm movements, and slip characteristics will be derived from the kinematic data.

Statistical Analysis Plan

For each variable, investigators will test for normality and employ the appropriate parametric or non-parametric descriptive statistics. Histograms and plots for each variable will be made and examined. Statistical hypothesis testing will be done using custom software written in R statistical computing language (R Core Team). General linear mixed-effects model will be used to determine the effects of diverse slip conditions on reactive movements and slip severity measures for all aims. This mixed-effects model will be used to include participants and order as random factors while testing for differences between conditions. For example, even though these data will have repeated measures from the same subject, a linear mixed effect model can resolve those non-independencies by including participants as a random factor and accounting for changes from baseline participant variation. Aim 1: independent variables will be a) turn radius (4 levels: no turn, 2m, 1m, 1/2m), b) slip timing (3 levels: early, mid, and late stance). Aim 2: independent variables will be a) slope (7 levels: no slope, ± 5.3 degrees AP, ± 10.6 degrees AP, ± 5.3 degrees ML, ± 10.6 degrees ML).

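### A participant random factor for baseline level alone leaves the radius, timing and slope tests miscalibrated if responses differ between participants; the Aim 2 model also omits timing

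*Combined protocol and SAP*

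**What the plan says.** The Statistical Analysis Plan proposes a general linear mixed-effects model for all aims. The model will "include participants and order as random factors while testing for differences between conditions". The justification is that "a linear mixed effect model can resolve those non-independencies by including participants as a random factor", and the factor is described as "accounting for changes from baseline participant variation". The plan names no participant-by-condition term, random slope, residual covariance structure or degrees-of-freedom method.

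For Aim 1 the fixed factors are turn radius and "slip timing (3 levels: early, mid, and late stance". For Aim 2 the list is slope alone: "Aim 2: independent variables will be a) slope (7 levels: no slope".

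The design is described in the aim-specific methods. In Aim 1, "participants slip both feet at 3 different times in the gait cycle for each of 3 path curvatures". In Aim 2, "participants slip at 3 different times in the gait cycle for each of 5 different uphill/downhill slopes", and the cross-slopes add "3 phases x 2 feet x 2 slopes that foot matters".

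**The concern.** There are two separate points, and they act in opposite directions.

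**Random part.** A random intercept gives all of a participant's slips the same correlation. If some people cope unusually badly with the tightest turn, their slips at that radius share an extra deviation that the intercept cannot absorb. The model then counts those slips as independent information about the condition. Its standard errors are too small, and the idiosyncrasies of a few participants can pass for a condition effect. A random order term does not supply the missing component.

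**Fixed part.** In Aim 2, timing is varied by design but not listed as a factor. Because timing is balanced within each slope, omitting it does not bias the slope comparison. It does inflate the residual, so a real slope effect can be missed. Foot on the cross-slopes does the same unless the ± mediolateral values are meant to code foot. In Aim 1, foot is varied but not listed.

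These are the only hypothesis tests that the plan describes.

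**Working it through.** **Inputs from the documents.** Aim 1: 3 radii × 3 timings × 2 feet = 18 slips per participant. Aim 2: 3 × 5 + 3 × 2 × 2 = 15 + 12 = 27. Both totals agree with the protocol. Each Aim 1 participant gives 18/3 = 6 slips per radius and 6 per timing. In Aim 2 it is 3 per level, uphill or downhill slope and 6 per cross-slope. The three radii of the Aim 1 methods were used.

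**Assumptions (not in the documents).** N = 20, alpha 5%, slip-to-slip SD 1, no true radius or slope effect. Let τ = participant-by-condition SD ÷ slip-to-slip SD, over 0 to 1.

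**Step 1: Aim 1 radius test, intercept only.** There are 18 × 20 = 360 slips. Residual df = 360 − 20 − 2 − 2 = 336, of which 2 × 19 = 38 carry participant-by-radius variation. Under the null hypothesis:

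- expected radius mean square = 1 + 6τ²
- expected residual mean square = [38(1 + 6τ²) + 298]/336

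With a correct model the two would be equal. The 5% critical value of F(2, 336) is 3.02. Dividing it by the ratio of the two mean squares and taking the tail area gives the approximate true error.

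| τ | Numerator | Denominator | Ratio | Approx. error | Simulated error |
|---|---|---|---|---|---|
| 0 | 1.00 | 1.00 | 1.00 | 5.0% | 5% |
| 0.1 | 1.06 | 1.01 | 1.05 | 5.8% | 6% |
| 0.25 | 1.375 | 1.042 | 1.32 | 10.3% | 10% |
| 0.5 | 2.50 | 1.170 | 2.14 | 24.5% | 25% |
| 1.0 | 7.00 | 1.679 | 4.17 | 48.5% | 49% |

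The simulated column is from 20,000 runs per setting. If timing responses vary too, the denominator becomes [76(1 + 6τ²) + 260]/336 and the simulated errors are 5/6/9.5/20/36%. Results at N = 10 and N = 30 agree within about 1.5 points, so recruiting more participants is no cure.

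The same point as a standard error for a radius contrast, both responses varying: true = √[2(τ² + 1/6)/20]; model = √(2 × residual mean square/120).

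| τ | Model | True | Shortfall |
|---|---|---|---|
| 0 | 0.129 | 0.129 | none |
| 0.25 | 0.134 | 0.151 | 11% |
| 0.5 | 0.149 | 0.204 | 27% |

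**Step 2: Aim 2 slope test, intercept only, nothing omitted (simulated).** At τ = 0/0.1/0.25/0.5/1.0: 5/6/10/24/55% if only slope responses vary; 5/6/8/17/34% if timing responses vary too.

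**Step 3: Omitted fixed effects.** Take three equally spaced timing means spanning 1.0 slip SD (−0.5, 0, 0.5). Their sum of squares over 27 × 20 = 540 slips is 540 × 0.5/3 = 90. Residual df = 540 − 20 − 6 = 514, so the residual mean square rises to 1 + 90/514 = 1.175. The critical value of F(6, 514) is 2.12. In effect it becomes 2.12 × 1.175 = 2.49, with tail area about 2.2%. The simulations, with only slope (or, in the last row, only radius) responses varying, are:

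| Omitted effect | τ = 0 | 0.1 | 0.25 | 0.5 | 1.0 |
|---|---|---|---|---|---|
| Aim 2, timing range 0.5 | 4% | 5% | 8% | 22% | 53% |
| Aim 2, timing range 1.0 | 2% | 3% | 5% | 17% | 49% |
| Aim 2, timing range 2.0 | 0.2% | 0.2% | 1% | 5% | 34% |
| Aim 2, foot difference 1.0 on cross-slopes | 3% | 4% | 6% | 19% | 51% |
| Aim 1, foot difference 1.0 | 2% | 3% | 6% | 18% | 43% |

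**Step 4: Both faults together.** In Aim 2, with timing range 1.0, foot difference 1.0, and slope and timing responses both varying, the listed model gives 1.4/1.4/2.8/9.3/27.6% (10,000 runs, no order term). A 300-run check in lme4 with a random order term (order SD 0.25) gave, for Aims 1 and 2, 3.3% and 4.7% at τ = 0.25 and 12% and 10% at τ = 0.5. Its Monte Carlo error is about 1 to 2 points.

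**Step 5: The fuller model.** REML with Satterthwaite degrees of freedom, both responses varying, 3,000 runs per setting: Aim 1 3.1/3.8/5.0/5.6/5.3%; Aim 2 with foot 4.4/4.2/5.0/5.4/5.4%. These REML figures were not rerun independently. Two other tests that carry participant-by-condition variation in the error term support them: the participant-by-radius mean square in Aim 1 and Hotelling's T² on slope means in Aim 2. They gave 4.6% to 5.3% in every setting.

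**The case against.** The plan gives no model formula. The intercept-only reading rests on one loosely worded phrase about baseline in a sentence offered as an example, and random slopes are not excluded. A mixed model can indeed resolve the dependence if it has suitable random terms. That stands, and it is why the sponsor is first asked to say what was intended. But baseline variation is the only function that the plan gives the participant factor.

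The size is unknown. Neither τ nor N is given, and at τ = 0.1 the effect is trivial. This also stands. Nothing in the documents supports a large τ, and nothing supports zero.

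The high error rates assume that nothing is omitted. With timing and foot omitted too, the Aim 2 test is conservative up to τ = 0.25, and at 0.5 the error is about 9%, roughly half the 17% found without those omissions. So the direction of the net error is undetermined. Two faults that offset each other by chance do not make a calibrated test.

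Foot in Aim 2 may already be coded. The ± values listed come to nine, which equals the number of slope-by-foot cells (5 + 2 × 2), although the label says seven levels. This is possible and needs a sentence of clarification. Timing is still absent.

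The proposed model is additive, and a foot effect might exist on curves only. With a foot difference of 2.0 SD on curves only, an approximation to the fuller Aim 1 model gave 2.5% at τ = 0 and about 4–5% from τ = 0.25. That is mild conservatism.

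**Conclusion.** The concern holds, conditionally. If participants differ in their response to condition, an intercept-only model is too liberal: with nothing omitted, about 8–10% at τ = 0.25 and 17–25% at τ = 0.5, against a nominal 5%. If they do not differ, the intercept suffices. Independently, leaving timing out of Aim 2 makes the slope test conservative, at about 2% for a timing range of one slip SD when τ = 0. The net direction cannot be determined from the documents. The figures rest on the assumed N, alpha and τ and on the intercept reading of the plan; the dependence on N is slight. The plan should be changed, because the correction is cheap and the design yields the replication that it needs. Confidence is medium, because the true size of τ is unknown.

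**What to change.** State the model in full:

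- **Aim 1:** fixed radius, timing and foot; random `(1|id) + (1|id:radius) + (1|id:timing)` plus the stated order term.
- **Aim 2:** fixed slope and timing, with foot modelled on the two cross-slopes (nine slope-by-foot cells, slope tested as a 6-df contrast among the seven slope means); random `(1|id) + (1|id:slope) + (1|id:timing)` plus order. Say whether the ± mediolateral values code foot.
- **Both:** Kenward-Roger or Satterthwaite degrees of freedom. Prespecify the variance components, do not select them by p-value, and remove one only if its variance is estimated at zero.

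If random responses to condition were already intended, a sentence saying so settles the first point.

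The cost is SAP wording and a few lines of R, with no extra data. If responses do not differ, the Aim 1 radius-contrast standard error is about 4% wider (0.134 against 0.129 at N = 20), and the test is mildly conservative when τ is small. Singular fits will be common in that range. At τ = 0/0.1/0.25/0.5/1.0, at least one participant-by-condition component was zero in 75/65/22/0/0% of Aim 1 fits and 74/62/13/0/0% of Aim 2 fits, so the zero-variance rule is needed. Foot should not be dropped from the Aim 2 remedy: without it, a foot difference of 1.0 takes the error to 2.8% at τ = 0.

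### Must the SAP say whether each outcome is an absolute post-slip value or a change from unperturbed gait before radius and slope effects can be tested?

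*Combined protocol and SAP*

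**What the plan says.** The Statistical Analysis Plan says the mixed model will determine the "effects of diverse slip conditions on reactive movements and slip severity measures for all aims". It names participants and order as random factors. It presents the participant factor as the way to deal with repeated measures from one person, that is, "including participants as a random factor and accounting for changes from baseline participant variation".

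The only list of outcomes is the last sentence of Aim 2 Specific Methods: "whole body angular momentum, COM characteristics, arm movements, and slip characteristics will be derived from the kinematic data". That sentence opens by giving its purpose, which is to measure what the slip does. Aim 1 has no list of its own. Neither section assigns a variable to the reaction or severity class, fixes an axis or frame, or states a reference.

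The design conditions are:
- Aim 1: "Data will be collected at a comfortable walking speed of 1.3 m/s", on a "straight path (infinite radius), or curved paths with radii of 2 or 1 meters". Also, "Only right turns will be examined".
- Aim 2: "Data will be collected with the treadmill set at a comfortable walking speed of 1.3 m/s", on "no slope, ± 5.0 and ± 10.0 degrees slopes in the direction of walking", plus 5.0 and 10.0 degree cross-slopes.

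**The concern.** Walking a tight curve or a slope differs from walking straight on the level even when nobody slips. If a COM or angular momentum outcome is the raw post-slip value, its contrast between conditions contains that steady-state difference as well as any difference in the response to the slip. If it is the change from unperturbed gait in the same condition, the steady-state part drops out. The SAP allows either, and its only wording about a baseline concerns participants, not conditions.

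Two analysts could therefore follow the same text and reach different answers, one reporting that radius or slope alters the reaction and the other reporting no effect. Because every turn is to the right, the shift does not average out over turn direction.

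**Working it through.** **Design counts.** Aim 1: 2 feet × 3 timings × 3 curvatures = 18 slips. Aim 2: 3 × 5 + 3 × 2 × 2 = 27 slips. Both match the protocol.

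**What the random factor does.** Write the outcome for participant i in condition c as y = μ + u_i + s_c + d_c + e, where s_c is the steady-state offset and d_c the slip response. The contrast with the reference condition is (s_c − s_0) + (d_c − d_0), because u_i cancels. In a simulated balanced data set, the two condition estimates were 0.72775967 and 1.00983499 both with and without the participant intercept. The factor removes none of s_c.

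**Size of the steady-state differences, Aim 1.** Inputs: v = 1.3 m/s and radii of 2 m and 1 m (protocol); g = 9.81 m/s² (physical constant). All values are zero on the straight path.
- Turn rate v/r: 0.65 and 1.30 rad/s, or 37.2 and 74.5 deg/s.
- Lateral acceleration v²/r: 1.69/2 = 0.845 and 1.69/1 = 1.69 m/s².
- Lean atan(v²/(g r)): atan(0.0861) = 4.9 and atan(0.1723) = 9.8 degrees.

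These values assume steady turning at exactly 1.3 m/s. The path has several turns of unstated arc length. As an example, a quarter-turn at 1 m is 1.57 m long and takes 1.57/1.3 = 1.2 s, about one stride at an assumed 1.0 to 1.2 s per stride. Steady state may not be reached, and speed is coached rather than mechanically fixed.

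**Size of the steady-state differences, Aim 2.** Vertical COM velocity relative to the stance foot is 1.3 × sin(5°) = 0.113 and 1.3 × sin(10°) = 0.226 m/s. On a treadmill the walker stays in place, so in the laboratory frame the mean is zero at every slope. This offset therefore depends on a choice of frame that the documents do not make. It also does not cover the cross-slopes, which take 12 of the 27 slips.

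The SAP lists a further 1/2 m radius and slopes of 5.3 and 10.6 degrees. That mismatch with the protocol is a separate matter, and the reasoning here is the same under either set.

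**Effect on the test (illustration only).** With an assumed COM height h of 1.0 m, the lateral offset h·v²/(g r) is 0.086 m at 2 m and 0.172 m at 1 m (0.155 to 0.190 m at 1 m for h of 0.9 to 1.1 m). The simulation had no true difference in reaction and used a repeated-measures F test.
- Absolute values, N = 20, participant-by-radius SD half the slip-to-slip SD: radius significant in 100%, 96.5% and 68% of runs at slip-to-slip SD of 0.10, 0.20 and 0.30 m.
- Absolute values over N = 10 to 30 and an SD ratio of 0 to 1: 17% to 100%.
- Deviations: 4% to 6%, as must happen when the inserted offset is subtracted.

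If the outcome is instead signed by the slipping foot, the shift cancels, because both feet slip at every radius.

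**Cost of referencing.** SE = √[(2/(mN))(1 + 1/k)], with k matched strides and m slips per condition: 6 in Aim 1, and 3 on the uphill/downhill slopes of Aim 2. Assumed: N = 20, a difference of 0.5 SD, stride SD equal to slip SD, and no participant-by-condition variance. The factor (1 + 1/k) is dropped for absolute values.

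| | Aim 1 power | Aim 2 power |
|---|---|---|
| Absolute | 97.2% | 78.2% |
| Deviation, k = 2 | 88.5% | 60.9% |
| Deviation, k = 10 | 95.8% | 74.3% |

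Aim 1 check: √(2/120) = 0.129 and 0.5/0.129 = 3.87, which gives 97.2%. With k = 2 the SE is 0.158, the ratio 3.16 and the power 88.5%.

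**The case for a change.** The strongest case for a change is that the omission can decide the answer. The absolute definition makes the null of no radius effect false before anyone slips. No sentence excludes that definition, and the no-turn and no-slope conditions cannot serve as an unperturbed reference because slips are delivered there too. A remedy would cost one line of text per outcome. Each slip follows 1 to 3 minutes of walking, and Aim 1 kinematics are recorded through the whole trial.

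Much of this stands: the classes are not assigned, no reference is stated, and the participant factor does not touch condition means. Four points limit it.
- The SAP never offers the participant factor as an adjustment for steady-state gait. Its stated job is non-independence, and it does that job.
- Arm movements and slip characteristics indicate their class by name. Angular momentum and COM characteristics are the two families left open.
- The stated purpose of measuring what the slip does, together with the term reactive movements, leans towards slip-attributable change without settling the matter.
- The total effect of a condition on the post-slip state is also a fair reading of the SAP's aim, and absolute values are the natural form for severity.

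**Conclusion.** No change to the plan is needed. This is a missing definition, not a rule that gives a wrong result. An absolute value estimates the total effect of the condition on the post-slip state. A deviation estimates the added response to the slip. Neither is an error, and the choice is a trade-off: the deviation removes the steady-state shift but adds noise. It also needs strides matched by phase and condition. Their number is not stated for Aim 1, and their capture is not confirmed for Aim 2.

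Analysts will have to choose a frame and a reference when they compute angular momentum and COM variables, and a report that names them lets the reader interpret a radius or slope effect correctly. Saying so in the SAP would be a courtesy for two outcome families.

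The accelerations of 0.845 and 1.69 m/s² rest on steady turning at exactly 1.3 m/s. The Aim 2 velocities exist only relative to the stance foot. The rejection rates rest on an assumed outcome, COM height, sample size and SDs, so they show that the two definitions can disagree, not how often they would in this study. The power figures rest on an assumed sample size, effect size and stride noise.

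### The Aim 1 model as listed has no term for slipped foot, so it cannot test whether the curvature effect differs between inside-foot and outside-foot slips

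*Combined protocol and SAP*

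**What the plan says.** **Design.** Under Aim 1 Specific Methods, participants "slip both feet at 3 different times in the gait cycle for each of 3 path curvatures for a total of 18 slip episodes". The curvatures delivered are a straight path and turns of 2 m and 1 m radius. The same section adds "Only right turns will be examined".

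**Model.** The Statistical Analysis Plan (SAP) describes one mixed-effects model for the "effects of diverse slip conditions on reactive movements and slip severity measures for all aims". It is to "include participants and order as random factors while testing for differences between conditions". The Aim 1 factors are then itemised: "Aim 1: independent variables will be a) turn radius (4 levels: no turn, 2m, 1m, 1/2m), b) slip timing (3 levels", with the three stance phases as the timing levels. The list stops there. Slipped foot does not appear in the SAP as a fixed effect, an interaction or a random factor. Neither averaging over feet nor a separate analysis for each foot is described.

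**Related text.** Aim 2 Specific Methods counts part of its episodes as "3 phases x 2 feet x 2 slopes that foot matters". That parenthesis sorts the Aim 2 slopes only and says nothing about turns. The same section lists the outcomes: "whole body angular momentum, COM characteristics, arm movements, and slip characteristics will be derived from the kinematic data". Neither it nor the SAP says which of these carry a sign, or whether they are mirrored according to the slipped side.

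**The concern.** Slipped foot is fully crossed with radius and timing, and it doubles the Aim 1 episodes from 9 to 18. Because every turn goes to the right, foot on the curved paths is also position: right is inside, left is outside. On the straight path there is no inside or outside. It is plausible from geometry that a slip of the inside foot and a slip of the outside foot call for different recoveries. That is an inference; the documents do not state it.

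If the listed model is followed literally, the two slips in each radius x timing cell are treated as replicates. Two things follow:

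- No contrast in the model asks whether curvature acts differently on inside-foot and outside-foot slips.
- Any real difference between the feet is counted as residual variation, which widens the standard errors for radius and timing.

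A narrower risk concerns signed outcomes. If an outcome is not mirrored by slipped side and the feet respond in opposite directions by similar amounts, the foot-averaged radius effect can cancel.

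**Working it through.** **1. The plan's own count.** 2 feet x 3 timings x 3 curvatures = 18, as stated. Without foot there are 3 x 3 = 9 cells, so each radius x timing cell holds 18/9 = 2 slips, one per foot. Curved-path episodes: 2 x 3 x 2 = 12. Straight: 6.

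**2. Assumed inputs.** The documents give no sample size, effect size or variance. Let *g* be the left-right gap on both curved radii, in residual SD, with no gap on the straight path. Take *n* = 10, 20, 40 and alpha 0.05. The calculations use participant, radius and timing and leave out the random order factor.

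**3. Bias with complete data.** Foot is balanced within every radius x timing cell, so omitting it shifts the radius coefficients by 0.

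**4. Precision.** Each curved-path slip deviates from its cell mean by ±g/2. That adds g²/4 on 12/18 of episodes, or g²/6, to the residual variance. The standard-error factor is √(1 + g²/6). Dividing instead by the residual df, 17n − 4, gives √(1 + 3g²n/(17n − 4)), which is almost the same.

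| g | √(1 + g²/6) | df version, n = 20 |
|---|---|---|
| 0.25 | 1.005 | 1.006 |
| 0.5 | 1.021 | 1.022 |
| 1 | 1.080 | 1.086 |

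**5. The test that is missing.** Radius x foot has 2 df. With gaps (0, g, g) and a gap that is the same in every participant, the noncentrality is n·g² and the error df are 17n − 7. If the gap at each radius also varies between participants with variance t, the noncentrality is n·(2/3)g²/(2/3 + t), with 2 and 2(n − 1) df.

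| g | Constant gap, n = 10 / 20 / 40 | t = 0.5, n = 10 / 20 / 40 |
|---|---|---|
| 0.25 | 10% / 15% / 27% | 7% / 10% / 17% |
| 0.5 | 27% / 50% / 81% | 15% / 29% / 55% |
| 1 | 81% / 98% / >99% | 49% / 84% / 99% |

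**6. What the listed model still finds.** Simulated at n = 20 (6,000 runs, constant gap). Entries are rejection rates.

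| Curved-path effect by foot (SD) | Radius term, listed model | Radius x foot, if added |
|---|---|---|
| +1.0 and +0.5 | >99% | 50% |
| +1.0 and 0 | 98% | 99% |
| +0.5 and 0 | 48% | 50% |
| +0.5 and −0.5 | 3% | 99% |

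The radius term fails only in the last row, where the feet cancel.

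**7. Uneven loss.** Suppose n = 20 and the outside-foot, late-stance, 1 m slip is missing in 25%, 50% or 100% of participants. The entries are the shift in the 1 m coefficient.

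| Model | Gap equal at all timings | Gap in late stance only |
|---|---|---|
| Radius + timing | 0.023g / 0.050g / 0.115g | 0.023g / 0.050g / 0.115g |
| + foot + radius x foot | 0 / 0 / 0 | 0.016g / 0.037g / 0.100g |
| + foot x timing as well | 0 / 0 / 0 | 0.006g / 0.013g / 0.042g |

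**The case against.** **The list may be shorthand.** This is the strongest reply, and much of it stands. The SAP lists do not match the protocol elsewhere. Aim 1 includes a 1/2 m radius that Aim 1 Specific Methods does not deliver. Aim 2 gives 5.3 and 10.6 degrees where Aim 2 Specific Methods gives 5.0 and 10.0. The list that begins "Aim 2: independent variables will be a) slope (7 levels" omits slip timing, which that aim crosses with every slope, and does not name foot. Its signed medial-lateral slopes might be a way of coding foot, although signed levels would make 9 conditions, not 7. So a reader who concludes that foot will certainly not be analysed goes further than the text. What can be said is that the model as written contains no foot term.

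**No stated objective is defeated.** This also stands. The documents give no foot hypothesis for turns and no reason for slipping both feet. Both may have been slipped so that the radius effect averages over them. If so, the SAP should say that.

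**The precision loss may be trivial.** Agreed for small gaps: about 0.5% at g = 0.25, and the effect is conservative.

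**Left and right turns are said not to differ.** That compares turn directions. It does not say that inside-foot and outside-foot slips are equivalent within a turn.

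**Order is already a random factor.** Trial order does not identify the slipped foot.

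**Conclusion.** The point holds as a gap in the written model, with moderate confidence. The Aim 1 design can estimate how the curvature effect depends on inside or outside foot, and the listed model cannot. The size of the loss is unknown, because it depends on a foot gap, a sample size and a variance that the documents do not give. Under the assumed gaps, standard errors rise by about 0.5% to 8%. Power for the omitted test runs from 7% (small, variable gap, n = 10) to above 99%.

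Three stronger readings are not supported:

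- *The radius results are biased.* With complete, balanced data the foot-averaged effect is unbiased. It is usually still detectable when both feet respond in the same direction. Cancellation needs opposite responses on an unmirrored outcome, and the documents do not say whether outcomes are signed or mirrored.
- *The protocol itself says how foot matters on turns.* Its remark about foot sorts the Aim 2 slopes and is silent on turns, either way.
- *Adding foot removes any effect of uneven loss.* The added terms reduce the shift. They remove it only if the foot gap is the same at every slip timing.

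**What to change.** In the Statistical Analysis Plan:

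1. Add to the Aim 1 list *c) slipped foot (2 levels: left, right)*, and add radius x foot, both as fixed effects. The SAP names no interactions, so radius x foot must be written out.
2. Report the radius effect by foot (inside and outside on the 2 m and 1 m paths) and averaged over feet.
3. State for each outcome whether it is signed and, if so, whether it is mirrored by slipped side.
4. Check the Aim 2 list for the same omission on the cross-slopes.

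Foot x timing can be added if the df allow; it further reduces the shift from uneven loss when the gap varies by timing. If the list was only abbreviated, the same wording settles the matter.

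**Cost.** One df for foot and 2 for radius x foot at the 3 delivered curvatures: 3 df out of 17n − 4. That is 3/166 = 1.8% at an assumed n = 10, 3/336 = 0.9% at n = 20 and 3/676 = 0.4% at n = 40. Foot x timing takes 2 more. No new slips are needed, because both feet are already slipped in every cell.
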